2.0 BACKGROUND

2.1 Introduction/Rationale for Development

2.1.1 Disease Under Study: Peripheral T-cell Lymphoma

Peripheral T-cell lymphomas (PTCL) are an uncommon group of disorders, accounting for about 10% of all non-Hodgkin lymphomas (NHL). EBV-associated extranodal NK/T-cell lymphoma (NKTCL) is more common in parts of Asia and South America, while angioimmunoblastic T-cell lymphoma (AITL) and peripheral T-cell lymphoma, not otherwise specified (PTCL NOS) are more common in Western countries.¹² TCLs are generally associated with poor outcomes after standard therapy, with variation in prognosis according to disease subtype.¹² ALK-expressing anaplastic large cell lymphomas (ALCL) have a favorable prognosis with 5-year survival exceeding 80%, though some studies suggest outcomes in ALCL are dependent on age rather than ALK status.¹²⁻¹⁴ Anthracycline-based induction combination chemotherapy is standard upfront treatment for patients with PTCL; however, with the exception of ALK-positive ALCL, relapse rates are high.¹⁵⁻¹⁷ Autologous hematopoietic stem cell transplantation (ASCT) is widely used as consolidation for PTCL patients in first remission to reduce the risk of relapse. Single-arm prospective and retrospective studies of consolidative ASCT for TCLs in 1st remission report improvements in survival compared to historical controls, but progression-free survival (PFS) remains low, ranging from 44-58% at 3-5 years.^{2,18-21} Outcomes are poorer in patients who undergo ASCT with relapsed PTCL, with 3-5 year PFS ranging from 32-41%.^{1,2}

Current approved therapies available for relapsed or refractory TCLs include histone deacetylase inhibitors (romidepsin and belinostat), pralatrexate, and brentuximab vedotin (for ALCL). With the exception of brentuximab vedotin for ALCL, these agents are associated with low response rates and short median progression free survival.³⁻⁵

In the pivotal PROPEL trial, 115 heavily pre-treated PTCL patients (median 3 prior systemic therapies) received pralatrexate as a single agent. The overall response rate (ORR) in 109 evaluable patients was 29%, including 12 (11%) complete responses (CR) and 20 (18%) partial responses (PR), with a median remission duration of 10.1 months. Median PFS and OS were 3.5 and 14.5 months, respectively. The most common grade 3/4 adverse events were thrombocytopenia (32%), mucositis (22%), neutropenia (22%), and anemia (18%).⁵

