10.0 STUDY CALENDAR

All procedures may increase in frequency if clinically indicated.

Table 10 Study Activity Calendar

Protocol Activity	Screening (Days) -28 to D1)	Protocol Therapy (Cycles) ^{a, c, m} (± 3 Days for all time points except g)														EOT ^p	Follow-up ^w			
		To be repeated (except e and l)							Safety post ^b								Response ^q (Every 12 weeks)		Survival ^r (Every 12 weeks)	
		1		2		3		4		5		6		7						
		D1	D8	D1	D8	D1	D8	D1	D8	D15 ^g	D1	D8	D1	D8	D1	D8				
Informed Consent	X																			
Eligibility Criteria	X																			
Registration	X																			
Medical History	X																			
Prior and Con. Med. review	X	X	X	X	X	X	X	X	X		X	X	X	X	X	X	X			
Post-study anti-cancer ther. status																	X	X	X	
Survival status		X	X	X	X	X	X	X	X		X	X	X	X	X	X	X	X	X	
Pembrolizumab		X		X		X		X			X		X		X					
Pralatrexate		X	X	X	X	X	X	X	X		X	X	X	X	X	X				
Leucovorin ^d		X	X	X	X	X	X	X	X		X	X	X	X	X	X				
Vitamin B12 ^e	X							X												
Folic acid ⁿ	X							X												
AE review		X	X	X	X	X	X	X	X		X	X	X	X	X	X	X	X		
Physical Exam.	X	X	X	X	X	X	X	X	X		X	X	X	X	X	X	X	X		
Vital signs ^f	X	X	X	X	X	X	X	X	X		X	X	X	X	X	X	X	X		
ECOG status	X	X	X	X	X	X	X	X	X		X	X	X	X	X	X	X	X		
Pregnancy Test ^o	X ^k	X		X		X		X			X		X		X		X	X ^s		
PT/INR and aPPT	X*																			
CBC w/diff, Plt	X*	X	X	X	X	X	X	X	X		X	X	X	X	X	X	X	X		
Serum Chemistry ^u	X*	X	X	X	X	X	X	X	X		X	X	X	X	X	X	X	X		

CONFIDENTIAL

Protocol Activity	Screening (Days -28 to D1)	Protocol Therapy (Cycles) ^{a, m} (± 3 Days for all time points except g)														EOT ^p	Follow-up ^w			
		To be repeated (except e and l)							Safety post ^b								Response ^q (Every 12 weeks)		Survival ^z (Every 12 weeks)	
		1		2		3		4		5		6		7						
		D1	D8	D1	D8	D1	D8	D1	D8	D15 ^g	D1	D8	D1	D8	D1					
Urinalysis ^x	x [*]																			
Thyroid Test ^v		x			x					x						x				
PET-CT or CT N/C/A/P ^h	x								x							x ^r		x		
Archival or Newly Obtained Tumor Tissue Collection	x ⁱ															x ⁱ				
Bone Marrow Aspirate and Biopsy ^j	x ^y							x ^l		x ^l						x ^t				
Correlative Blood Collection		x	x					x ^l		x ^l										

* Tests to be performed within 28 days of treatment initiation.

- In the absence of a delay due to toxicity, each treatment cycle lasts 21 days ± 3 days.

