- k. Female subjects of childbearing potential should have a negative urine or serum pregnancy within 72 hours prior to receiving the first dose of study medication.
- l. Do not repeat this time point for correlative blood collection: peripheral blood is collected prior to study treatment/procedures on C1D1, C2D1, C4D1, C5D1, and at EOT (see also footnote t).
- m. Day 8 labs/visits are set up because of pralatrexate administration on these days. If a patient discontinues pralatrexate (and continues with pembrolizumab alone), these Day 8 labs/visits can be omitted.
- n. Folic acid supplementation is to begin within 10 days (as early as possible) prior to the first dose of pralatrexate administration (per pralatrexate product insert). However, if folic acid was not taken but MMA (methylmalonic acid) and HCY (homocysteine) levels were checked and are in normal range at screening, the investigator can decide to start study therapy immediately. Administration should continue during the full course of pralatrexate therapy and for 30 days after the last dose of pralatrexate. Refer to [Section 5.13.2](#).
- o. If the urine test is positive or cannot be confirmed as negative, a serum pregnancy test will be required. Pregnancy testing will also be performed whenever an expected menstrual cycle is missed or when pregnancy is otherwise suspected.
- p. Assessments to be performed within 10 days of treatment discontinuation (except tumor imaging, see footnote r). Assessments performed after last dose of study agent and within 7 days of the decision to end treatment may serve as EOT assessments.
- q. For participants yet to progress. Follow-up will occur every 12 weeks (-/+ 7 days) starting from last on-treatment scan. After one year, the imaging time point will occur every 18 weeks (+/- 7 days). Response Follow-up will be performed until progression or off study, and for at least one year in each patient who did not progress yet.
- r. PET-CT (or CT) at time of discontinuation (EOT) will only be performed in patients who discontinue treatment for disease progression. Note: if a previous scan was obtained within 4 weeks prior to the date of discontinuation, then repeating the scan at treatment discontinuation is not mandatory. For patients who discontinue treatment for other reasons than disease progression (e.g. for toxicity, CR): PET-CT (or CT) will not be performed at EOT and will be performed 12 weeks

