11.2 Clinical Endpoint Definitions

Overall Response Rate (ORR): Defined as the proportion of patients that have a documented CR or PR at any time during study treatment.

Complete Response (CR) rate: Defined as the proportion of patients that have a documented CR at any time during study treatment.

Duration of Response (DOR): Defined as the time from the first achievement of PR or CR to time of PD. Patients who never achieve PR or CR are excluded. Patient who has not had disease progression/relapse at last follow-up is censored at the time of last follow-up.

Overall Survival (OS): Defined as time from initiation of study therapy to death from any cause. If a patient is alive at the last evaluation time period, survival time is censored at the time of last follow-up.

Progression-Free Survival (PFS): Defined as the time from initiation of study therapy to the first observation of disease relapse/progression or death from any cause, whichever occurs first. If the patient has not progressed relapsed or died, the patient is censored at the time of last follow-up.

Toxicity: Toxicity and adverse events will be recorded using the NCI CTCAE 5.0 scale. Observed toxicities will be summarized by type (organ affected or laboratory determination such as absolute neutrophil

count), severity (by NCI CTCAE v5.0 and nadir or maximum values for lab measures), date of onset, duration, reversibility, and attribution.

Unacceptable Toxicity: defined as one of the following AEs that is at least possibly related to study treatment:

- Any **≥ grade 3 immune-related AE (IrAE)** that does not resolve to grade ≤ 1 within 7 days with the exception of:
 - Grade 3 immune-related hepatitis if ALT or AST < 8 x ULN or total bilirubin < 5 x ULN.
 - Grade 3 asymptomatic endocrinopathy.
 - Inflammatory response attributed to local antitumor response.
 - Vitiligo or alopecia of any grade.
- Any non-hematologic **grade 4 AE** that does not resolve to grade ≤ 1 within 7 days with the exception of:
 - Grade 4 asymptomatic lipase or amylase without evidence of pancreatitis
 - Grade 4 asymptomatic laboratory abnormalities including, but not limited to, hypo- or hyperglycemia, hypo- or hypernatremia, hypo- or hyperkalemia, hypo- or hypermagnesemia, hypo- or hyperphosphatemia, or hyperuricemia that do improve within 48 hours to Grade ≤ 2 with supportive measures.
 - Inflammatory response attributed to local antitumor response.
- Any Grade 5 AE.

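### DOR has no rule for new anticancer therapy, so remission after a later transplant or drug counts towards the regimen; median PFS is essentially unaffected

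*Combined protocol and SAP*

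**What the plan says.** **Endpoint definitions (Section 11.2).** DOR is "Defined as the time from the first achievement of PR or CR to time of PD". Its only censoring rule is "Patient who has not had disease progression/relapse at last follow-up is censored at the time of last follow-up". PFS runs to the "first observation of disease relapse/progression or death from any cause, whichever occurs first"; otherwise "the patient is censored at the time of last follow-up". New anticancer therapy is neither an event nor a censoring point for either endpoint. Death is an event for PFS but not for DOR.

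**Analysis (Section 12.3.3).** DOR, PFS and OS are estimated by Kaplan-Meier. No rule for later therapy is added.

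**Follow-up (Section 5.11 and Table 10).** Starting new anticancer therapy can end safety follow-up. Response Follow-up, for patients who have not progressed, has no such limit. Footnote q says "Response Follow-up will be performed until progression or off study", with a minimum of one year for those still progression-free. Footnote r deals with early stops without progression: "For patients who discontinue treatment for other reasons than disease progression (e.g. for toxicity, CR"). These patients are next scanned 12 weeks after their last scan and then follow the follow-up schedule.

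**Data.** Table 10 has a row for "Post-study anti-cancer ther. status". No analysis uses it.

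**Removal from study (Section 5.13.1).** Other antineoplastic therapy is prohibited from Day 1 to the end of protocol therapy. Participants who need it are to be taken off the study.

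**The concern.** The secondary objective is to estimate DOR and PFS in patients treated with this combination. With no rule for later therapy, the DOR clock keeps running for a patient who stops in remission and starts something else. Take a patient first in PR at the cycle 4 scan, transplanted 3 months later and in remission until month 36. That patient has a DOR of about 33 months, of which 3 came before the transplant. A patient who stops for toxicity while in PR and switches drug before PD is treated the same way.

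Responders will be few: 24 × 29% ≈ 7 at the cited single-agent response rate, and 24 × 50% = 12 if the ORR were 50%. Two or three such patients could shape the upper part of the DOR curve. The trial has one arm, so no control group shows how much of the remission is due to later treatment.

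**Working it through.** The plan states no target, event count or precision for DOR or PFS, so there is no figure of its own to reproduce here. The calculation below illustrates size only.

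**Inputs**
- DOR without later therapy: exponential, median 10.1 months (single-agent pralatrexate figure, Section 2.1.1).
- PFS after transplant: Section 2.1.1 says "Outcomes are poorer in patients who undergo ASCT with relapsed PTCL, with 3-5 year PFS ranging from 32-41"%. It does not say which percentage goes with which year. The two extremes are used: 32% at 3 years and 41% at 5 years.
- Transplant 3 months after first response, in a share f of all responders, f = 10-40%. Both are assumptions.
- Transplant is unrelated to prognosis. This is also an assumption.

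**Hazards per month**
- Before or without transplant: λ = ln 2 / 10.1 = 0.0686
- After transplant: μ = −ln(0.32)/36 = 0.0317, or −ln(0.41)/60 = 0.0149

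**DOR curve beyond 3 months**

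S(3) = exp(−3λ) = 0.814, and for t > 3

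S(t) = (0.814 − f)·exp(−λ(t−3)) + f·exp(−μ(t−3))

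At 24 months exp(−21λ) = 0.2366, and exp(−21μ) = 0.5144 or 0.7319. For example:
- f = 20%, μ = 0.0317: 0.614 × 0.2366 + 0.20 × 0.5144 = 0.145 + 0.103 = 0.248
- f = 40%, μ = 0.0149: 0.414 × 0.2366 + 0.40 × 0.7319 = 0.098 + 0.293 = 0.391

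The median solves S(t) = 0.5.

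| Share of responders transplanted | Median DOR, months | 24-month DOR |
|---|---|---|
| 0% | 10.1 | 19% |
| 10% | 10.7-11.0 | 22-24% |
| 20% | 11.3-12.2 | 25-29% |
| 30% | 12.1-13.8 | 28-34% |
| 40% | 13.0-16.0 | 30-39% |

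Censoring at transplant returns 10.1 months and 19% in every row. That follows from assuming independence and does not validate censoring.

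**PFS**

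Assume non-responders have an exponential PFS with median 2.5 months, and response is recorded at 2.8 months (4 cycles × 21 days = 84 days). Then

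S_PFS(t) = ORR·S(t − 2.8) + (1 − ORR)·exp(−t·ln 2/2.5)

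where S = 1 before response and S(u) = exp(−λu) up to 3 months after it. For f from 0 to 40%:

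| ORR | Median PFS, months | 24-month PFS, f = 0 | 24-month PFS, f = 10-40% |
|---|---|---|---|
| 29% | 4.0 throughout | 6.9% | 7.7-12.4% |
| 50% | 5.9-6.0 | 11.7% | 13.1-21.3% |

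The median barely moves because transplant comes at 2.8 + 3 = 5.8 months. By then overall PFS is 0.29 × 0.814 + 0.71 × 0.200 = 38% at ORR 29%, and 0.50 × 0.814 + 0.50 × 0.200 = 51% at ORR 50%.

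**The case against.** The strongest reply is that following patients to PD regardless of later therapy is a legitimate treatment-policy estimand, and that censoring at transplant may be informative. This stands. It is why Section 11.2 should be kept, but the plan does not declare that choice; it is silent.

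Second, Section 5.13.1 could be read as covering the leading case: a patient who needs other antineoplastic therapy is removed, goes off study under footnote q, and is censored before transplant. This stands in part. The prohibition ends with protocol therapy, and Section 5.11 sends all participants into follow-up. It therefore does not reach a responder who has already stopped for toxicity or CR, and sites could reasonably differ on the rest.

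Third, frequency is unknown. No section plans transplant after response, Section 5.10 does not list it as a reason for stopping, and the rationale in Section 2.5 describes transplant as rescuing few patients. The 40% row implies 0.40/0.814 = 49% of those still in remission at 3 months, which nothing in the documents supports. At 10-20% the median moves by 0.6-2.1 months. That is less than a 12-week scan interval and well inside the sampling error of a median from 7-12 responders (SD about 4-6 months by simulation). This stands as a limit on importance. The shift nevertheless favours the regimen whenever remission lasts longer after transplant than without it, and under DOR as defined a death in remission after transplant is censored rather than counted.

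A reader might also infer three stronger points that the documents do not support:
- That the comparison with the cited 3.5-month median PFS is distorted. The median does not move, and post-transplant deaths count as PFS events, so the net effect on PFS could be in either direction.
- That ORR, limited to study treatment, is inconsistent with DOR. ORR limits when a response may be counted; DOR necessarily extends beyond treatment.
- That the 10.1-month benchmark was computed under a different rule. The documents do not say how that study handled later therapy.

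**Conclusion.** The point holds for DOR. Followed as written, Sections 11.2 and 12.3.3 credit the regimen with remission that continues under later therapy, and the follow-up schedule allows such cases to occur. Over the assumed 10-40% range, median DOR rises by about 0.6-5.9 months and 24-month DOR by about 3-20 percentage points. These sizes depend on the assumed transplant share and timing, the pairing of post-transplant percentages with years, and independence of transplant from prognosis.

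For PFS only the tail is affected, in a direction that cannot be fixed in advance. The primary ORR and the Gehan stopping rule are untouched, and neither DOR nor PFS drives a decision in this trial. This is a worthwhile, low-cost improvement to secondary endpoints, not a flaw in the design.

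**What to change.** Keep the Section 11.2 analysis and add to Section 12.3.3, for example:

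> DOR and PFS will also be estimated with patients who start new anticancer therapy, including stem cell transplant, before PD censored at their last disease assessment before that therapy. Both estimates will be reported, with the number of patients affected.

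Two supporting changes are needed:
- Confirm that the post-study therapy item in Table 10 records a start date. The table lists only a status.
- Reconcile Sections 5.11 and 5.13.1 with Table 10 footnotes q and r on whether starting new therapy takes a patient off study, so that all sites follow patients alike.

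The cost is a short text addition, one further Kaplan-Meier run per endpoint and, if it is not already captured, one date field. No visit, scan or sample size changes. The downside is that censoring at new therapy may be informative, since patients chosen for transplant may differ in prognosis from those who are not. The estimate should therefore supplement the 11.2 analysis and not replace it. Fixing the rule now also avoids choosing it after the remissions are known.

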5.5 Definition of Dose-Limiting Toxicity

The dose-limiting toxicity (DLT) observation period will be 2 cycles of therapy, from the start of Cycle 1 through the start of Cycle 3, including any delays (regardless of cause) to start of C3. It will be 42 days if there is no delay. If C3D1 is shorter than 42 days from C1D1, DLT will be evaluated through prior to administration of study therapy on C3D1.

Toxicities will be graded according to the National Cancer Institute Common Terminology Criteria for Adverse Events (CTCAE, Version 5.0) accessible at:

https://ctep.cancer.gov/protocolDevelopment/electronic_applications/ctc.htm#ctc_50

DLT will be defined as one of the following AEs that is **at least possibly related** to study treatment:

Hematologic

- Grade 4 neutropenia lasting > 7 days (despite the use of growth factor support).
- Grade 4 thrombocytopenia lasting > 7 days or requiring platelet transfusion.
- Grade 3 or 4 thrombocytopenia associated with grade 2 or higher bleeding.
- Grade 4 anemia not associated with lymphoma.
- Any Grade 5 AE.

Non-hematologic

- Grade \geq 3 pneumonitis without suspected infectious cause.
- Any \geq grade 3 AE that does not resolve to grade \leq 1 within 7 days with the exception of:
 - Grade \geq 3 asymptomatic laboratory abnormalities, including lipase or amylase, that do not require hospitalization or delay of treatment.
 - Grade 3 nausea or vomiting, that improves to grade \leq 2 within 7 days with supportive measures.
 - Grade 3 fatigue that improves to grade \leq 2 within 14 days with supportive measures.
 - Grade 3 asymptomatic endocrinopathy of any duration.
 - Grade 3 fatigue related to endocrinopathy that resolves within 7 days of hormone-replacement or corticosteroid therapy.
 - Grade 3 inflammatory response attributed to local antitumor response of any duration.
 - Vitiligo or alopecia of any grade and duration.
- Any Grade 5 AE

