AST / ALT elevation or Increased bilirubin	Grade 2	
 Withhold pembrolizumab Hold pralatrexate 	
 Administer corticosteroids (initial dose of 0.5- 1 mg/kg prednisone or equivalent) followed by taper 	
 Monitor with liver function tests (consider weekly or more frequently until liver enzyme value returned to baseline or is stable)
	Grade 3 or 4	
 Permanently discontinue pembrolizumab Hold pralatrexate 	
 Administer corticosteroids (initial dose of 1-2 mg/kg prednisone or equivalent) followed by taper 	

Type 1 diabetes mellitus (T1DM) or Hyperglycemia	Newly onset T1DM or Grade 3 or 4 hyperglycemia associated with evidence of β -cell failure	
 Withhold pembrolizumab 	
 Initiate insulin replacement therapy for participants with T1DM Administer anti-hyperglycemic in participants with hyperglycemia 	
 Monitor participants for hyperglycemia or other signs and symptoms of diabetes.
Hypophysitis	Grade 2	
 Withhold pembrolizumab 	
 Administer corticosteroids and initiate hormonal replacements as clinically indicated. 	
 Monitor for signs and symptoms of hypophysitis (including hypopituitarism and adrenal insufficiency)
	Grade 3 or 4	
 Withhold or permanently discontinue pembrolizumab¹ 		
Hyperthyroidism	Grade 2	Continue pembrolizumab	
 Treat with non-selective beta-blockers (eg, propranolol) or thionamides as appropriate 	
 Monitor for signs and symptoms of thyroid disorders.
	Grade 3 or 4	Withhold or permanently discontinue pembrolizumab ¹		
Hypothyroidism	Grade 2, 3, or 4	Continue pembrolizumab	
 Initiate thyroid replacement hormones (eg, levothyroxine or liothyroinine) per standard of care 	
 Monitor for signs and symptoms of thyroid disorders.
Nephritis and Renal dysfunction	Grade 2	
 Withhold pembrolizumab Hold pralatrexate 	
 Administer corticosteroids (prednisone 1-2 mg/kg or equivalent) followed by taper. 	
 Monitor changes of renal function

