Because of the unique immune-related adverse events (IrAEs) observed with checkpoint inhibitors, we will monitor for "unacceptable toxicity" (defined in [Section 11.2](#)) and treatment-related mortality at any time during study treatment with this new combination of drugs. This monitoring will include all patients treated on the study regardless of the dose levels they were on. The expected rate of "unacceptable toxicity" should not be >33%. If the rate of "unacceptable toxicity" is >33% after at least 6 patients are treated on study at any bi-annual safety review, or if a 2nd death that is at least possibly related to study treatment occurs regardless of the number of patients on study, accrual will be halted and a full review of these events will be performed by the City of Hope Data Safety Monitoring Committee (DSMC). Patient accrual will not resume until approved by the DSMC to do so. These rules are in addition to the bi-annual review of all toxicities submitted to the City of Hope Data Safety Monitoring Committee (DSMC). Patients with ongoing toxicity will be followed until resolution or stability.

In addition, because of the evidence that PD-1 may act as a tumor suppressor in preclinical T-cell lymphoma models and the recent reports of rapid disease progression in patients with ATLL, a subtype of PTCL, we will also monitor for rapid progression of disease. If at any bi-annual safety review during the conduct of the study, and after at least 3 patients are treated on study, > 33% of patients who received at least one dose each of pembrolizumab and pralatrexate (regardless of the dose level or if during the phase 1 or phase 2 portion of the study) experience rapid progression (i.e. an acceleration of disease activity with disease progression according to the 2014 Lugano classification prior to completion of 3 cycles of study therapy), the study accrual will be halted and a full review of these events will be performed by the City of Hope Data Safety Monitoring Committee (DSMC). Patient accrual will not resume until approved by the DSMC to do so.

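### The hepatitis exception in the unacceptable-toxicity definition joins its limits with *or*, so the 8 x ULN limit has no effect while bilirubin is below 5 x ULN and sites can classify the same event differently

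*Combined protocol and SAP*

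**What the plan says.** Section 11.2 counts as unacceptable toxicity an immune-related event of grade 3 or higher, at least possibly related to treatment, "that does not resolve to grade ≤ 1 within 7 days with the exception of" a short list. The first item on that list is "Grade 3 immune-related hepatitis if ALT or AST < 8 x ULN or total bilirubin < 5 x ULN".

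Section 12.3.4 uses this definition as the numerator of its halting rule. Accrual stops for review by the data safety monitoring committee (DSMC) if the rate "is >33% after at least 6 patients are treated on study at any bi-annual safety review". On the denominator it says: "This monitoring will include all patients treated on the study regardless of the dose levels they were on". A separate limb halts accrual on a second "death that is at least possibly related to study treatment occurs regardless of the number of patients on study".

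Two other places deal with the same kind of event:

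- **Table 6.3**, row "AST / ALT elevation or Increased bilirubin": at grade 3 or 4, pembrolizumab is permanently discontinued and pralatrexate is held.
- **Section 5.5** (dose-limiting toxicity, DLT): there is no hepatitis exception. The nearest is a general one for grade 3 or higher "asymptomatic laboratory abnormalities, including lipase or amylase, that do not require hospitalization or delay of treatment".

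The synopsis only points to Section 11.2. No section restates the hepatitis exception with *and*.

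**The concern.** A numeric limit in an exception should separate exempt cases from counted ones. With *or*, the transaminase limit does so only when bilirubin is also at or above 5 x ULN. A case with bilirubin below that is exempt whatever ALT and AST are within grade 3. Conversely, a case with both transaminases below 8 x ULN is exempt whatever the bilirubin is within grade 3.

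Section 12.3.4 says that the rule exists because of immune-related toxicity. A definition that drops persistent immune hepatitis on one favourable value works against that purpose. Ambiguity adds a second problem: if sites read the sentence differently, the observed rate depends partly on which site reported the event.

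**Working it through.** **1. Logic of the exception.** For a grade 3 case still unresolved after 7 days, three readings are possible:

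- *Literal*: exempt if ALT < 8, or AST < 8, or bilirubin < 5 (x ULN).
- *Narrower*: exempt if both transaminases < 8, or bilirubin < 5.
- *All limits*: exempt only if ALT < 8, AST < 8 and bilirubin < 5. A parameter-by-parameter reading comes to the same thing.

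| ALT | AST | Bilirubin | Literal | Narrower | All limits |
|---|---|---|---|---|---|
| <8 | <8 | <5 | exempt | exempt | exempt |
| <8 | <8 | ≥5 | exempt | exempt | counts |
| <8 | ≥8 | <5 | exempt | exempt | counts |
| <8 | ≥8 | ≥5 | exempt | counts | counts |
| ≥8 | <8 | <5 | exempt | exempt | counts |
| ≥8 | <8 | ≥5 | exempt | counts | counts |
| ≥8 | ≥8 | <5 | exempt | exempt | counts |
| ≥8 | ≥8 | ≥5 | counts | counts | counts |

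Exempt combinations: 7 of 8, 5 of 8 and 1 of 8. These are logical cells, not probabilities. Under both *or* readings, every row with bilirubin below 5 x ULN is exempt.

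**2. Effect on the halting rule.** The plan states no operating characteristics for this rule, so there is no figure to reproduce. Inputs:

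- Threshold >33% from 6 patients on: Section 12.3.4.
- Looks at n = 6, 10, 14, 18, 22, 26, 30: assumed. Section 12.2 expects 30–36 patients in 48 months, which is 8 half-years, so 30/8 = 3.75 to 36/8 = 4.5 patients per bi-annual review.
- Other unacceptable toxicity, u = 30%: assumed.
- Affected patients, h: persistent grade 3 hepatitis exempt under *or* but counted under *all limits*, with no other unacceptable toxicity. Assumed at 1%, 2%, 5% and 10%.

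The smallest counts with k/n > 0.33 are 2, 4, 5, 6, 8, 9 and 10 at the seven looks. Let p be the counted rate: p = u if affected cases are exempt, p = u + h if they count. Carry forward the exact distribution of events among trials not yet halted, adding Binomial(4, p) between looks. At each look, move the probability at or above the smallest count into the halted total.

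| Affected (h) | Counted rate p | P(halt by 30) | Gain over 0.733 |
|---|---|---|---|
| not counted | 30% | 0.733 | – |
| 1% | 31% | 0.761 | 0.028 |
| 2% | 32% | 0.788 | 0.055 |
| 5% | 35% | 0.858 | 0.125 |
| 10% | 40% | 0.937 | 0.204 |

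**3. Sensitivity.** If 33% is taken as exactly one third, 2/6, 6/18 and 10/30 no longer trigger. The figures become 0.58 not counted, against 0.62, 0.65, 0.75 and 0.88. With u = 20% and the 0.33 cutoff, they are 0.40 not counted, against 0.43, 0.47, 0.57 and 0.73.

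**4. What the documents say about h.** Section 6.1.1 lists pembrolizumab hepatitis below 1% and raised AST/ALT at 1–10%, without restricting either to severe or persistent events. Section 6.1.2 notes hepatic toxicity with pralatrexate but gives no rate. No rate is given for the combination.

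**The case against.** The strongest reply is that the sentence is shorthand: a transaminase event is exempt below 8 x ULN, and a bilirubin event is exempt below 5 x ULN. Table 6.3 names its row in the same style. On that reading a case with ALT above 8 x ULN counts, and nothing is wrong except the drafting. This stands as a possible intent, and it is why the sponsor must confirm. It does not remove the point, because the literal words say something else and no section decides between them.

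A reader might infer from the truth table that almost all grade 3 immune hepatitis escapes the rule. The documents do not support that as a statement about patients. The eight cells are not equally likely, and no section gives the distribution of laboratory values.

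A reader might also take the fall from 0.94 to 0.73 as the size of the problem. It needs 10% of patients to have the affected kind of hepatitis. That is the top of the band that Section 6.1.1 gives for any AST/ALT increase with pembrolizumab. The combination could be higher than pembrolizumab alone, but nothing in the documents shows it.

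Table 6.3 is tempting as proof that *or* is wrong, since an exempt event can still end pembrolizumab. It does not isolate the connector: a grade 3 case below all the limits would stay exempt and still end pembrolizumab after the change. A treatment rule for one patient and an accrual trigger for the trial may also differ on purpose.

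Finally, other safeguards remain. The exception covers grade 3 only. Persistent non-hematologic grade 4 events (with their own exceptions), grade 5 events, DLTs in phase 1 and the second related death are handled separately. Liver-test abnormalities meeting Section 7.3.3 are reported expeditiously, and the DSMC reviews all toxicities bi-annually. Affected cases therefore miss one automatic trigger, not all oversight.

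**Conclusion.** The definition is defective as written. On a literal reading, bilirubin below 5 x ULN alone exempts a persistent grade 3 immune hepatitis, and the 8 x ULN limit then has no function. On the other available reading, all values must be below their limits. Because the definition feeds a numeric halting rule, the reading has to be fixed in advance.

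The impact is probably modest. At 1–2% of patients affected, the chance of a halt differs by about 3 to 6 percentage points; at 5%, by about 12; at 10%, by about 20. These figures rest on 30% other unacceptable toxicity, no overlap between the two kinds of event, and looks about four patients apart. At 1–2%, the full rate of 31–32% is still below the protocol's 33% limit. At 5% it is 35%, over the limit, while only 30% is counted. The direction does not depend on these assumptions; the size does.

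**What to change.** In Section 11.2, keep the protocol's own limits and state the connector so that each has effect in the halting-rule numerator: exempt grade 3 immune-related hepatitis only if ALT and AST are both < 8 x ULN and total bilirubin is < 5 x ULN. The sponsor should confirm that this is the intent. If it is not, the sponsor should write out the intended rule so that every site applies the same one.

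In the same amendment, reconcile Section 11.2 with the DLT definition in Section 5.5 and the liver row of Table 6.3, or say why they differ. Sections 5.10 and 12.1 also name unacceptable toxicity as a reason to end protocol therapy, without citing Section 11.2. A short note that the change concerns only the Section 12.3.4 count would prevent confusion. No treatment rule changes.

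The cost is a one-line amendment. A few more events may count toward a pause, which the DSMC can review and lift.
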